9.2.4. Baseline Value

The Baseline value is defined as the last non-missing value collected on or prior to first dose.

9.2.5. Body Mass Index

The BMI is derived as follows: $\text{weight (kg)} / [\text{height (cm)} / 100]^2$

9.2.6. Change from Baseline

Change from Baseline will be calculated as: post-Baseline assessment value – Baseline assessment value when both values are not missing.

Percent change from Baseline is calculated as (change from Baseline/Baseline result * 100).

If either the Baseline or the post-Baseline result is missing, the change from Baseline and/or percentage change from Baseline is set to missing. Additionally, if the Baseline is 0, the percentage change from Baseline will be missing.

9.2.7. Medications and Therapies

Medications/therapies with administration dates and times on or after the date and time of the first study drug dose are considered concomitant. If the start date of a medication or therapy is partially or completely missing and the end (stop) date and time of the medication/therapy does not indicate that it occurred prior to first dose, then the determination of concomitant status will be based on the following:

If the start year is after the year of the first study drug dose, then the medication/therapy is concomitant; else, if the start year is the same as the year of the first study drug dose and the start month is missing, then the medication/therapy is concomitant; else if the start month is present and is the same or after the month of the first study drug dose, then the medication/therapy is concomitant; else, if the start date is completely missing, then the medication/therapy is concomitant.

All other medications/therapies are considered prior medications/therapies and could occur from 14 days prior to study enrollment up through the Screening Period and prior to the first dose.

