7.1.4. Prior and Concomitant Medications/Therapies

Prior medications will be defined as medications that were discontinued prior to the start of study drug. Concomitant medications will be defined as medications that either started prior to first dose of study drug and were continuing at the time of first dose of study drug or started on or after the date of the first dose of study drug. If it cannot be determined whether a medication was stopped prior to the start of study drug dosing due to partial or missing medication start or end dates, it will be considered a concomitant medication.

The World Health Organization (WHO) Drug Dictionary version from March 2018 or later will be used to code the medications. Medications will be summarized by Anatomical Therapeutic Chemical (ATC) level 3 class and generic drug name.

Prior and concomitant medications will be summarized separately for the FA Set by cohort and overall. The number and percentage of participants receiving any concomitant medication will be summarized, as well as the number and percentage receiving any concomitant medication by ATC drug class and generic drug name. Participants reporting use of more than 1 medication at each level of summarization (any medication received, ATC class, and generic drug name) will be counted only once. All ATC class terms will be displayed alphabetically and generic drug names within each ATC class will be displayed by descending order of incidence. Prior medications used to treat WD and an additional analysis of all prior medications will be summarized similarly. WD treatment history will be summarized by counts and percentages for Cohort 1 and Cohort 2 by prior WD medication, where prior WD medication is defined as the later of the treatment at the time of Screening or most recent treatment prior to Screening and is categorized as penicillamine, trientine hydrochloride, zinc, or combination.

Prior and concomitant medications will be presented in a data listing by patient and medication name.

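### For partial start dates, SAP 9.2.7 decides prior or concomitant status from the start date alone, so some medications that SAP 7.1.4 makes concomitant are classed as prior

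*SAP*

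**What the plan says.** SAP 7.1.4 decides by whether the medication had stopped:

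- Prior: "Prior medications will be defined as medications that were discontinued prior to the start of study drug".
- Concomitant: any medication begun on or after first dose, and any that "started prior to first dose of study drug and were continuing at the time of first dose of study drug".
- Default: "If it cannot be determined whether a medication was stopped prior to the start of study drug dosing" because dates are partial or missing, the medication is concomitant.

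SAP 9.2.7, among the technical specifications for derived variables, decides differently. It opens with: "Medications/therapies with administration dates and times on or after the date and time of the first study drug dose are considered concomitant". It then takes medications whose start date is partly or wholly missing and whose stop date "does not indicate that it occurred prior to first dose, then the determination of concomitant status will be based on the following". The branches that follow return concomitant for a start year after the first-dose year, for the first-dose year with the month missing, for a start month the same as or after the first-dose month, and for a wholly missing start date. Everything else goes to the residual rule: "All other medications/therapies are considered prior medications/therapies".

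**The concern.** No branch of the 9.2.7 tree asks whether the medication was still being taken at first dose. The tree mirrors the rule for treatment-emergent adverse events in SAP 9.2.1. For an adverse event, onset is the right test. For a medication it is not: a drug begun before dosing and carried through it is concomitant, as 7.1.4 says.

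The two sections can therefore give opposite answers for the same record, and the SAP does not rank them. At stake are the separate prior and concomitant summaries that 7.1.4 plans by cohort and overall. If programming follows the appendix, the affected medications are counted in the first and are absent from the second.

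**Working it through.** The SAP gives no figure to reproduce, so the check applies both rules to the same records.

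**Inputs.** The 7.1.4 definitions and the 9.2.7 branches set out above. First dose is taken as June 2021. This is an assumption for illustration; only the order of the dates matters. In every record the stop date does not show that use ended before first dose: the medication is either continuing or has no stop date.

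**Two readings of the month branch.** In 9.2.1 the month test sits under the condition that the start year equals the first-dose year (nested). In 9.2.7 the branches run on as prose, so the month test can also be read as free-standing (flat). Both readings are shown, with the partial-date tree applied as written.

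| Recorded start | 9.2.7 nested | 9.2.7 flat | 7.1.4 |
|---|---|---|---|
| 2018, month missing | prior | prior | concomitant |
| March 2018, day missing | prior | prior | concomitant |
| September 2018, day missing | prior | concomitant | concomitant |
| March 2021, day missing | prior | prior | concomitant |
| June 2021, day missing | concomitant | concomitant | concomitant |
| 2021, month missing | concomitant | concomitant | concomitant |
| Wholly missing | concomitant | concomitant | concomitant |

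**Result.** The tree conflicts with 7.1.4 in 4 of 7 patterns (nested) or 3 of 7 (flat). These are counts of date patterns, not shares of records. Only the September 2018 pattern depends on the reading: its year is earlier, but its month number is not before June.

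**Internal check.** A wholly unknown start gives concomitant, while a start known to lie years earlier gives prior, although neither medication is known to have stopped. Knowing more about the start moves the record to the wrong class.

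**What one record can do.** With approximately 10 participants (SAP 9.1), moving one participant out of a table row changes the overall percentage by about 1/10, or 10 points, and by more within a cohort. This happens only if the participant has no other medication counted in that row, because each participant is counted once per level.

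**The case against.** **The opening sentence of 9.2.7 already covers ongoing use.** A medication recorded as ongoing is being given after first dose, so that sentence can be read to make it concomitant before the tree is reached. This stands in part. It weakens the conflict for records marked ongoing, although the next sentence sends partial-start records to their own determination. It does not help where the stop date is missing, since no administration after first dose is then documented. The residual sentence also goes on to describe prior use as lying between 14 days before enrollment and first dose, which suggests that its authors had pre-dose use in mind; the branches do not enforce that.

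**SAP 7.1.4 is the main text and states the right rule.** True, but the SAP does not say that it prevails, and 9.2.7 is where a programmer would look for the derivation.

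**Few records will be affected.** Protocol 6.5.2 bars most medicines from before Day -7. Chelators stop from Day -4 and zinc at least 21 days before Day 1, so both should normally have known stop dates before dosing. This is fair, and the number may be small. It need not be zero: Protocol 6.5.1 allows medically indicated medicines, and Protocol 10.4.1 allows hormonal contraception.

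**Nothing is lost.** SAP 7.1.4 lists every prior and concomitant medication by patient, and SAP 7.1.2 handles protocol deviations separately. This stands and limits the consequence.

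**Conclusion.** The inconsistency is real and minor. As written, the 9.2.7 tree gives a classification that contradicts the SAP's own definition when the partial start date lies in an earlier year with the month missing, in an earlier year with an earlier month number, or in an earlier month of the first-dose year. An earlier-year start with the same or a later month number is affected only on the nested reading. The result reaches the tables only if programming follows 9.2.7 rather than 7.1.4.

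A reader might infer more than the documents support:

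- That long-term medicines in general drop out of the concomitant table. The tree applies only to partial or missing start dates.
- That every ongoing medication with a partial start before the first-dose month is misclassified. The flat reading and the opening sentence of 9.2.7 both leave exceptions.
- That a number of misplaced entries can be estimated. The documents give no count of such records.
- That screening for disallowed or confounding agents would fail. Neither document assigns that use to the concomitant table.

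The effect is limited to the descriptive prior and concomitant medication tables. Copper balance does not use this classification.

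**What to change.** Amend SAP 9.2.7 so that status depends on the stop date:

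- A medication is prior only if its stop date, including a partial stop year or month, is definitely before first dose.
- A medication that is ongoing, or whose stop date is missing or indeterminate, is concomitant whatever its start date. One started on or after first dose is concomitant in any case.

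A lighter alternative is one sentence in 9.2.7 stating that 7.1.4 governs. Either way the SAP's existing definition is kept. The cost is SAP wording and a small programming change.

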9.2.8. Visit Windowing

In analysis of data summarized by study visit, all data collection will be reassigned a study visit where data is scheduled for collection based on the actual days relative to Baseline. All visits will be assigned a target study day. Baseline will have a target study day of 1. For each assessment, the post-Baseline Period will be divided up using the scheduled visit's target day. The lower bound of each visit interval will be evaluated as the mid-point between the target day and the previous visit's target day in the following manner: $\text{study day interval lower bound} = \text{ceiling}(\text{target study day} - ((\text{target study day} - \text{last target study day})/2))$. [Table 3](#) shows an

example of visit windowing that will be used to summarize by-visit vital sign data. Other data will be summarized similarly in accordance to their SoA (**Protocol Table 1**).

Table 3: Visit Windows used to Summarize by-Visit Vital Signs Data

Scheduled Visit	Target Study Day	Study Day Interval
Baseline	1	Last measurement on or prior to first dose of study drug
Day 9	9	2 to 15
Day 23	23	16 to 31
Day 40	40	32+

If more than one value is mapped to the same scheduled visit, the closer of those values will be considered for summarization. If multiple records exist with the same distance from the target study day, the last occurrence will be used. Visit windows are intended to be contiguous such that all data collected at all post-Baseline visits, whether scheduled or unscheduled, will map to one of the visits.

The visit displayed on data listings will be reflective of the scheduled visit label as reported on the CRF. Study days relative to Baseline will be displayed for each visit so it is apparent which visit the data may have been reassigned to in the summaries.

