- ^k A full physical examination will be performed at Screening, at check-in for the study, and at the End of the study/Early Termination Visit. A physical examination should also be performed on any participants with ongoing adverse events prior to discharge from the unit. Otherwise, a symptom-driven physical examination may be performed at other times, at the Principal Investigator's discretion.
- ^l Height at screening only.
- ^m While in the CRU, study intervention will be administered after an overnight fast (ie, at least 10 hours) at the same time every morning; drug is to be administered with 240 mL of water and meals should be delayed a minimum of 2 hours after dosing. As an outpatient, participants are expected to take ALXN1840 at approximately the same time daily (+/-1 hour). Participants should take the medication with a glass of water on an empty stomach; meals should be delayed a minimum of 2 hours after dosing.
- ⁿ During the outpatient period, participants will use SMS text messaging to confirm study intervention administration.
- ^o Blood sampling for PK/PD will occur before ALXN1840 administration and represents a predose trough. See [Table 2](#) for PK/PD sampling on Days 1, 25, 29, and 39.
- ^p PK/PD collection will include timepoints described in the schedule of PK/PD assessment for Days 1, 25, 29, and 39 ([Table 2](#)).
- ^q Samples for serum chemistry will be obtained following a fast of at least 8 hours at the Screening Visit and at check-in. In case of rechecks, and postdose serum chemistry, participants may not have fasted for 6 or 8 hours before the serum chemistry sample is taken.
- ^r Laboratory assessment including chemistry, hematology, and coagulation parameters should be performed on Days -8, -1, 8, 23, and 28 only.
- ^s Menstruation check is for women only; women of childbearing potential should only be enrolled after a negative serum pregnancy test result at Screening. Additional urine pregnancy testing will be standard for the protocol unless serum testing is required by site policies, local regulation, or Institutional Review Boards (IRBs)/Independent Ethics Committees (IECs) (Section 10.2). In addition to pregnancy tests detailed at the visits in the SoA, females of childbearing potential will be required to perform urine pregnancy tests at least every 4 weeks at their home or the study site throughout their time in the study.

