3. In this study, dosing for ALXN1840 will be initiated at 15 mg once daily for a minimum of 4 weeks, with an increase to 30 mg after 4 weeks, unless there are safety concerns that, in the opinion of the Investigator(s) and/or Alexion, may place participants at undue risk, in which case, patients may remain on the 15 mg/day dose for the duration of the study.	
 • Dose range limit 15 mg every other day to 30 mg/day
4. The dose should be decreased or interrupted if any of the relevant Dose Modification criteria are met (Table 7).	
 • Dose range limit 15 mg every other day to 30 mg/day

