4. DESCRIPTION OF THE PROTOCOL

[figure not shown]
Study ALXN1840-WD-204 will be conducted as an open-label, repeat-dose study to evaluate the effects of ALXN1840 on copper balance in participants with Wilson Disease (WD).

Treatment-experienced (which includes standard of care therapies or ALXN1840) and treatment-naïve participants are eligible for this study. Eligible patients will be classified into one of two cohorts:

- Cohort 1 (treatment experienced): Patients who have received WD therapy for > 28 days
- Cohort 2 (treatment naïve): Patients who have received WD therapy for ≤ 28 days

Following Screening and enrollment, participants will check-in to the clinical research unit (CRU) on Day -8 for the Run-in Period. The purpose of the Run-in Period is to support diet equilibration (Day -7 through Day -5) and measure pretreatment copper and molybdenum balance (Day -4 through Day -1). Participants will remain on a copper/molybdenum-controlled diet throughout both the Inpatient Period 1 (Day -8 to Day 9) and Inpatient Period 2 (Day 23 to Day 40). The study design schematic is presented in Figure 1. While not in the CRU, participants will be encouraged to adhere to their usual copper-controlled diet.

Figure 1: Study Design Schematic

1. Participants eligible for the study will be enrolled on Day -7 and initiated on a copper- and molybdenum-controlled diet, which will be continued during Treatment Period 1 and Treatment Period 2 when in the CRU, through Day 39.
2. Participants will be admitted to the CRU for Treatment Period 1 on Day -8 and may be discharged on Day 9 or remain in the CRU for their own safety or to maintain the integrity of the conduct of the study. Participants who are discharged will be re-admitted on Day 22 or Day 23 for Treatment Period 2 and will remain in house until Day 40. To ensure flexibility, the Outpatient Period may be extended up to an additional 14 days with Investigator approval. In this situation, participants will be given additional study drug to support daily dosing throughout the Outpatient Period. In such cases, the actual Outpatient Period duration will be recorded and the participant will continue Inpatient Period 2 at Day 23.
3. Participants will be administered ALXN1840 at a dose of 15 mg/day on Day 1 through Day 28 and then increase to 30 mg/day on Day 29 through Day 39.
4. Participants will have 3 intake and output collection periods including:
 - Baseline Day -4 through Day -1

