7.3.3. Other Safety

7.3.3.1. Analyses for Laboratory Tests

Actual values and changes from treatment Baseline will be summarized descriptively for participants with available data for each laboratory parameter by cohort and overall. Missing laboratory data will not be imputed and only scheduled assessments will be included in by-visit summaries. All data, including that which is only collected at Screening, will be included in data listings. Laboratory measurements will be listed separately by participant, laboratory test, unit, and visit.

Laboratory parameter values will be graded according to the National Cancer Institute Common Terminology Criteria for Adverse Events (CTCAE). Shift tables by treatment will be produced for these laboratory parameters. These tables will summarize the number of participants with each baseline grade relative to the reference ranges and changes to the worst highest grade assessed post dose during the study.

Summary results for shift will include the count and percentage of participants within each shift category by scheduled visit. Laboratory values outside the normal range will also be summarized and assessed for trends indicating a safety signal. Additionally, a summary and listing of liver enzyme elevation will be presented and an evaluation of drug-induced serious hepatotoxicity plot will be created.

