9.2.3. Analysis Relative Day

Analysis relative day is the day relative to the first dosing day. It will be calculated as: analysis date – first dose date + 1 if analysis date is after the first dose date, or else as: first dose date – analysis date.

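### SAP visit windows run on actual days and ignore the permitted outpatient extension, so Day 23 (15 mg) vital signs can be reported as Day 40; the relative-day formula and the End of Study window also need correcting

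*SAP*

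**What the plan says.** **Windowing (SAP 9.2.8).** For by-visit summaries, "all data collection will be reassigned a study visit where data is scheduled for collection based on the actual days relative to Baseline". Each window's lower bound is the midpoint between its target day and the previous target, rounded up. Table 3 gives the vital-sign windows: Day 9 = 2 to 15, Day 23 = 16 to 31, Day 40 = 32 or later. Other data follow the same method on their own schedules. When values compete, "If more than one value is mapped to the same scheduled visit, the closer of those values will be considered for summarization"; ties go to the last occurrence. The CRF visit label is kept in listings only.

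**Extension (SAP section 4; Protocol 4.1 and Table 4).** The Outpatient Period may be lengthened by up to 14 days. "In such cases, the actual Outpatient Period duration will be recorded and the participant will continue Inpatient Period 2 at Day 23".

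**Relative day (SAP 9.2.3).** One is added to the date difference only "if analysis date is after the first dose date, or else as: first dose date" minus analysis date.

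**Use.** SAP 7.3.3.2 summarises vital-sign changes at each visit. SAP 7.3.3.1 adds for laboratory data: "Summary results for shift will include the count and percentage of participants within each shift category by scheduled visit".

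**Schedule (Protocol Table 1).** Vital signs are marked at Days 9, 23 and 40 and at End of Study (Day 54 ± 2). Dosing is 15 mg/day through Day 28 and 30 mg/day from Day 29.

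**The concern.** After an extension, protocol day and actual day differ for the rest of the study. The SAP names visits by protocol day but assigns values to them by actual day.

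Dose rises on a fixed protocol day, so in a by-visit table the visit label is how the reader infers the dose. A value moved from Day 23 to Day 40 is a 15 mg value read as a 30 mg one. With about 10 participants, also split by cohort, one such participant can visibly change a row.

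Two related rules are faulty without any extension. The relative-day formula does not separate days before first dose from days on treatment, and the last vital-sign window absorbs the End of Study visit.

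**Working it through.** **1. Reproducing Table 3.** Lower bound = ceiling(target − (target − previous target)/2):
- Day 23: ceiling(23 − 14/2) = 16, as printed.
- Day 40: ceiling(40 − 17/2) = ceiling(31.5) = 32, as printed.
- Day 9: ceiling(9 − 8/2) = 5, but 2 is printed. The printed value matches the statement that windows are contiguous after Baseline. Nothing below depends on it.

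**2. Vital signs with extension e.** Day 23 falls on actual day 23+e and Day 40 on 40+e. Day 23 enters the Day 40 window when 23+e ≥ 32, that is e ≥ 9. Its distance from target 40 is then 17−e, against e for the true Day 40 value.

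| e | Day 23 value: actual day (distance from 40) | True Day 40 value: actual day (distance) | Reported as Day 23 | Reported as Day 40 |
|---|---|---|---|---|
| 0–8 | 23–31 (own window) | 40–48 (0–8) | Day 23 | Day 40 |
| 9 | 32 (8) | 49 (9) | none | Day 23 |
| 10 | 33 (7) | 50 (10) | none | Day 23 |
| 11 | 34 (6) | 51 (11) | none | Day 23 |
| 12 | 35 (5) | 52 (12) | none | Day 23 |
| 13 | 36 (4) | 53 (13) | none | Day 23 |
| 14 | 37 (3) | 54 (14) | none | Day 23 |

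**3. Urinalysis.** Scheduled on Days 8, 14–18 (taken here as Day 16), 23, 26–28 (taken as Day 28), 40 and 54. Lower bounds are ceiling(23 − 3.5) = 20, ceiling(28 − 2.5) = 26, ceiling(40 − 6) = 34 and ceiling(54 − 7) = 47.
- Day 23 leaves its window when 23+e ≥ 26, so the window is empty from e = 3. For e = 3–10 the Day 23 sample is reported as Day 28.
- Day 28 enters the Day 40 window when 28+e ≥ 34 (e ≥ 6). At e = 6 both values are 6 days from target and the later, true Day 40 value is kept. At e = 7–14 the true Day 40 sample (actual 47–54) is in the End of Study window, and the Day 28 sample (15 mg) is reported as Day 40.

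**4. Chemistry and haematology.** The schedule also marks these in the Day 30–35, Day 40 and End of Study columns, yet its footnote r says: "Laboratory assessment including chemistry, hematology, and coagulation parameters should be performed on Days -8, -1, 8, 23, and 28 only".
- With Day 40 but no Day 30–35 sample, the result is the same e = 7–14.
- With a Day 30–35 sample, its window starts at 29, 31 or 32 if it is taken on Day 30, 33 or 35. The Day 28 sample is then reported under that 30 mg visit from e = 2, 3 or 4. (On Day 30, e = 1 is a tie and the later value is kept.)
- If footnote r is literal, the last window is Day 28 = 26 or later. The Day 23 sample is |e − 5| days from target and the Day 28 sample e days, so Day 23 displaces Day 28 from e = 3; both are 15 mg.

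**5. Relative day, SAP 9.2.3 as written.**

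| Protocol day | −8 | −4 | −3 | −2 | −1 | 1 | 2 | 3 | 4 | 8 |
|---|---|---|---|---|---|---|---|---|---|---|
| Computed | 8 | 4 | 3 | 2 | 1 | 0 | 2 | 3 | 4 | 8 |

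Numbers 2, 3 and 4 each denote one pre-dose and one on-treatment balance day, and the Day −8 and Day 8 laboratory samples share the number 8. SAP 7.2.1 uses signed days, and 9.2.8 gives Baseline a target day of 1.

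**6. End of Study.** Without an extension, actual days 52–56 lie in the Day 40 window, 12 to 16 days from target. The value is dropped if a Day 40 value exists and reported as Day 40 if not.

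**The case against.** The strongest counter-argument is about consequence. The extension is optional and needs Investigator approval. No inferential safety analysis is planned. SAP section 7 allows listings alone if numbers are too small, and listings show both the CRF visit label and the study day, so a reassignment can be traced. The worst-grade shift tables by treatment do not depend on windows. PK/PD concentration summaries carry dose. Baseline is protected because "The Baseline value is defined as the last non-missing value collected on or prior to first dose". All of this stands, and it confines the problem to by-visit safety summaries, including the additional shift counts by visit.

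The laboratory figures also rest on assumptions: the SAP gives no target day for the outpatient sample, and no End of Study window for urinalysis. If the outpatient sample has no window of its own, the Day 23 lower bound becomes ceiling(23 − 15/2) = 16. A sample from Days 16–18 could then fill the Day 23 window, so that window need not be empty. The Day 23 and Day 28 samples are still misplaced over the same ranges. With an open-ended Day 40 window, e = 7–14 also survives: the Day 28 sample is 12−e days from target, in absolute value, against e.

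Table 3 is called an example, but it is also said to be what will be used for vital signs. On relative day, the dosing day is not strictly without a rule: it falls into the second branch and returns 0. No summary result is shown to change through that formula; the harm is to displayed study days, on which 9.2.8 relies to make reassignment visible.

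A last point is that subtracting the extension only from Inpatient Period 2 leaves unscheduled values taken during the extension on actual days. Such a value cannot displace a true Day 40 value at distance 0, though it could stand in for a missing one.

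**Conclusion.** The concern holds. For vital signs the result is exact from the printed windows and selection rule: no misassignment by extension at 0–8 days; at 9–14 days the Day 23 value is reported as Day 40, the true Day 40 value is lost and Day 23 is empty. For laboratory data, misplacement starts at about 2 to 4 days. A 15 mg sample appears under a 30 mg visit at 7–14 days, or from 2–4 days if a Day 30–35 sample is taken. Those figures depend on the schedule assumptions stated in the working; under the literal reading of footnote r no dose boundary is crossed.

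The relative-day and End of Study faults do not need an extension. The effect is on descriptive by-visit safety tables. The balance periods in SAP 7.2.1 are labelled by protocol day and dose and would be affected only if programmed on actual days, which the SAP does not state. The number of participants extended is not given. This should be corrected, but it does not threaten the primary result as documented.

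**What to change.** Three SAP edits:

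1. **9.2.3.** Relative day = date − first dose date + 1 on or after first dose; date − first dose date before it. Day −4 then gives −4 and the dosing day gives 1.
2. **9.2.8.** From Inpatient Period 2 onward, window on protocol day: actual day minus the recorded extension. State that the 7.2.1 periods use the same day. Keep actual days since first dose as a separate variable for the treatment-duration analysis. Protocol day also serves participants with no first 30 mg dose to anchor on, since Protocol Table 4 says "patients may remain on the 15 mg/day dose for the duration of the study" where there are safety concerns.
3. **Table 3, in protocol days.** Day 40 = 32 to 46; End of Study (target 54) = 47 or later, from ceiling(54 − 14/2) = 47.

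Make edits 2 and 3 together. An End of Study row on actual days alone would push the true Day 40 value out of its window from e = 7 (40 + 7 = 47). With both edits, each scheduled vital-sign visit maps to its own window for every e from 0 to 14. One further sentence, that values dated before readmission cannot be assigned to a visit after Day 23, would deal with unscheduled samples.

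The cost is SAP text and programming. Dates and extension lengths are already recorded, so no new data are needed.
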